10.3.2. Definition of SAE

If an event is not an AE per definition above, then it cannot be an SAE even if serious conditions are met (e.g., hospitalization for signs/symptoms of the disease under study, death due to progression of disease).

A SAE is defined as any untoward medical occurrence that, at any dose:
a. Results in death
b. Is life-threatening The term “life-threatening” in the definition of “serious” refers to an event in which the participant was at risk of death at the time of the event. It does not refer to an event that hypothetically might have caused death had it been more severe.
c. Requires inpatient hospitalization or prolongation of existing hospitalization In general, hospitalization signifies that the participant has been detained (usually involving at least an overnight stay) at the hospital or emergency ward for observation and/or treatment that would not have been appropriate in the physician’s office or outpatient setting. Complications that occur during hospitalization are AEs. If a complication prolongs hospitalization or fulfills any other serious criteria, the event is serious. When in doubt as to whether “hospitalization” occurred or was necessary, the AE should be considered serious. Hospitalization for elective treatment of a pre-existing condition that did not worsen from baseline is not considered an AE.
d. Results in persistent disability/incapacity 
 • The term disability means a substantial disruption of a person’s ability to conduct normal life functions. • This definition is not intended to include experiences of relatively minor medical significance such as uncomplicated headache, nausea, vomiting, diarrhea, influenza, and accidental trauma (e.g., sprained ankle) that may interfere with or prevent everyday life functions but do not constitute a substantial disruption.
e. Is a congenital anomaly/birth defect

f. Other situations:

- Medical or scientific judgment should be exercised in deciding whether SAE reporting is appropriate in other situations such as important medical events that may not be immediately life-threatening or result in death or hospitalization but may jeopardize the participant or may require medical or surgical intervention to prevent one of the other outcomes listed in the above definition. These events should usually be considered serious.

Examples of such events include invasive or malignant cancers, intensive treatment in an emergency room or at home for allergic bronchospasm, blood dyscrasias, or convulsions that do not result in hospitalization, or development of drug dependency or drug abuse.

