7. STUDY INTERVENTION DISCONTINUATION AND PARTICIPANT DISCONTINUATION/WITHDRAWAL

7.1. DISCONTINUATION OF STUDY INTERVENTION

Study intervention for an individual participant may be permanently discontinued at any time at the discretion of the Investigator.

Study intervention for an individual participant must be temporarily interrupted and may be permanently discontinued for the following, as determined by the DSMC:

- any severe AE possibly, probably, or definitely related to study intervention

Study intervention for an individual participant will be permanently discontinued for any of the following:

- any SAE possibly, probably or definitely related to study intervention
- any of the changes in hepatic function detailed in Section 7.1.1
- pregnancy, as detailed in Section 10.4

Re-challenge with study intervention is not allowed.

Discontinuation from study intervention does not mean discontinuation from the study.

Remaining visits and study procedures should be completed as indicated by the SoA.

Additionally, participants in whom study intervention is prematurely discontinued will be followed until Uox returns to $\geq 80\%$ of baseline. Hematology, clinical chemistry, urinalysis, and pregnancy testing (as detailed in **Table 3**) and 24-hour urine collections will be repeated monthly. Should this follow-up take more than 6 months, participants will be re-consented for additional follow-up.

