8.1.6.1. Kidney Stone Events and Stone Burden

Participants will provide a 12-month history of stone events at Screening and will report any stone events during the study.

For the purpose of this study, “stone events” are all events that meet one or more of the following criteria:

- **renal stone requiring medical intervention** (e.g., outpatient procedures such as lithotripsy, or hospitalization and/or inpatient surgical intervention for confirmed stone-related pain and/or complications);
- **stone passage with or without hematuria;**
- **renal colic requiring medication.**

Concurrent events will be defined as events occurring within the same 4-week (28-day) window.

Note: Although the number of stone events is an efficacy endpoint, stone events will be considered AEs of special interest (Section 10.3.3), as participants may enter the study with pre-existing stones.

For the purpose of the study, “stone burden” is a term used primarily as a metric for quantifying and qualifying changes from baseline in the overall number and 2-dimensional surface area of renal stones, as observed via kidney ultrasound over the course of the study.

Taken together, the terms stone event and stone burden will be used to derive meaningful quantification and qualification of overall impact of clinical sequelae of renal stones during the course of the trial.

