10.3.3. Definition of Adverse Event of Special Interest

An AESI is a noteworthy event for the particular product or class of products that a Sponsor may wish to monitor carefully ([CIOMS VI, 2005](#)).

Events Meeting the AESI Definition:**Injection site reaction (ISR):**

An ISR is a disorder characterized by an intense adverse reaction (usually immunologic) developing at the site of an injection. Potential ISRs will be graded as follows:

Signs or symptoms at the injection site (e.g., erythema, swelling) with a time to onset of 4 or more hours from the time of study intervention administration will be evaluated according to the Common Terminology Criteria for Adverse Events (CTCAE) v 5.0 criteria for ISR, detailed below. If any of the CTCAE criteria for ISR are met, the event will be recorded as an ISR and graded in accordance with **Table 4**. If the criteria are not met, individual signs or symptoms will be recorded as AEs and graded in accordance with the intensity categories detailed in Section 10.3.4.

Table 4: Grading of Injection Site Reactions, CTCAE v 5.0

Grade 1	Grade 2	Grade 3	Grade 4	Grade 5
Tenderness with or without associated symptoms (e.g., warmth, erythema, itching)	Pain; lipodystrophy; edema; phlebitis	Ulceration or necrosis; severe tissue damage; operative intervention indicated	Life-threatening consequences; urgent intervention indicated	Death

Individual signs or symptoms at the injection site with a time to onset of less than 4 hours from the time of study intervention administration will be recorded as AEs (not as an ISR) and graded in accordance with the intensity categories detailed in Section 10.3.4.

Muscle pain or weakness

Because the nonclinical safety program in mice identified potential off-target effects on skeletal muscle, participants should be monitored for signs and symptoms of muscle weakness or pain, in addition to measurement of plasma CK.

Kidney Stone Events

Patients with PH are predisposed to the development of multiple and recurrent urinary tract and kidney stones. As participants may enter the study with pre-existing stones, stone events (as defined in Section 8.1.6.1), while being considered in the evaluation of efficacy, will be considered AESI.

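### The bracketed examples in protocol 10.3.2 present hospitalization for the disease and death from progression as non-AEs; 10.3.1 gives no such exemption, and 8.1.6.1 and 10.3.3 class hospitalized stone events as AEs of special interest

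*Protocol*

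**What the plan says.** Protocol 10.3.2 opens with a conditional rule: "If an event is not an AE per definition above, then it cannot be an SAE even if serious conditions are met". The sentence runs straight on into a bracket, so that such an event "cannot be an SAE even if serious conditions are met (e.g., hospitalization for signs/symptoms of the disease under study". The bracketed examples of the kind of event meant are, in full: "hospitalization for signs/symptoms of the disease under study, death due to progression of disease". Criterion (c) of the same section makes an event serious if it "Requires inpatient hospitalization or prolongation of existing hospitalization".

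Protocol 8.1.6.1 defines stone events to include stones needing medical intervention, with these examples: "outpatient procedures such as lithotripsy, or hospitalization and/or inpatient surgical intervention for confirmed stone-related pain and/or complications". It calls stone events AEs of special interest (AESI). Protocol 10.3.3 repeats that stone events, "while being considered in the evaluation of efficacy, will be considered AESI".

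Protocol 7.1 lists among the reasons for permanent discontinuation of study intervention "any SAE possibly, probably or definitely related to study intervention".

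**The concern.** The examples tell a site that a disease-related admission is not an AE and so cannot be an SAE. The rest of the protocol treats the disease-related event it names most explicitly, the stone event, as an AE, and lists hospitalization within its definition. The same admission can therefore be classified in two ways, depending on whether the site reads the rule or its example.

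Four things depend on the serious classification:

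- **Expedited reporting.** Under 8.3.4, SAEs reach the sponsor within 24 hours. Under 10.3.5 they go on a separate SAE form, which an ordinary AE entry does not replace.
- **The collection window.** Under 8.3.1, AEs are collected to the end of study and SAEs to 30 days after the last day of participation. A stone admission in those 30 days is collected only if it is regarded as an SAE.
- **The SAE tables.** SAP 9.1 reports treatment-emergent SAEs with a risk difference and 95% confidence interval, and SAP 9.1.2 tabulates them by system organ class and preferred term.
- **The related-SAE rule in 7.1**, which takes its input from the same definition.

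Late reporting or non-reporting of an SAE is also on the SAP's major protocol deviation list. A site that followed the protocol's own example could be recorded as having a major deviation.

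**Working it through.** No figure in the plan is at issue, so the check sets the passages side by side.

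**Step 1. Is there a basis for the examples in the definition they refer to?** The 10.3.1 list of events not meeting the AE definition has four kinds of entry:

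- laboratory or other safety-assessment findings associated with the disease, unless more severe than expected;
- procedures (the condition that led to the procedure is the AE);
- admissions where nothing untoward occurred;
- expected fluctuations of existing conditions that do not worsen.

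None of these exempts an admission for symptoms of the disease, or a death from its progression. The part of 10.3.1 on events that do meet the definition has a parenthesis about progression of underlying disease. It is attached to abnormal test results and safety assessments, not to clinical events.

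**Step 2. What do the other passages say about disease-related events?**

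| Place | Content | Direction |
|---|---|---|
| 10.3.2, bracketed examples | Admission for the disease and death from progression shown as non-AEs | Not an SAE |
| 10.3.1 | Exacerbation of a chronic condition is an AE | AE |
| 10.3.1 | Clinical sequelae of lack of efficacy are reported if they fit the definitions | AE or SAE |
| 8.3.1 | Deterioration of a condition present at screening is recorded as an AE | AE |
| 8.1.6.1 and 10.3.3 | Stone events, hospitalized ones included, are AESI | AE |
| 8.3.3 | Follow-up rule covers SAEs and non-serious AESI | An AESI can be serious |
| 10.3.2(c) | Inpatient hospitalization is a seriousness criterion | SAE |

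**Step 3. Apply the full rule to a stone event with inpatient admission.** It is an AE (8.1.6.1, 10.3.3), so the condition that opens 10.3.2 is not met and the exclusion does not apply. Criterion (c) is met. The event is an SAE.

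**Step 4. Apply the example alone.** The admission is for signs or symptoms of the disease under study, so it is shown as a non-AE that cannot be an SAE.

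Steps 3 and 4 disagree for the same event. The conflict lies between the example and the AE classification. AESI status and SAE status are not alternatives.

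**Step 5. What is lost if a site follows Step 4?** During the study, the event should still reach the AE case report form: SAP 8.4 counts stone events from it. SAP 9.1.3 summarizes them by type and maximum severity, not by seriousness, so those tables would not reveal a missing serious flag. After the last visit only SAEs are collected, so there the whole event could be missed. The treatment-emergent window in SAP 6.1.9 ends at study completion. The in-study case therefore affects the treatment-emergent SAE tables, and the post-study case affects SAE reporting and listings.

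**Possible origin.** The protocol amendment history records that a progression-of-disease item was removed from the 10.3.1 list and names only 10.3.1 as affected. The bracketed examples may be a leftover from that item. The conflict exists in the current text without this explanation.

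**The case against.** The strongest reply is that the text already settles the case. The exclusion is conditional, stone events are expressly AEs, and 10.3.2 adds that doubtful hospitalizations count as serious. The bracket might also be meant for admissions without worsening, such as the elective admissions that 10.3.2 exempts. The first part is right about the correct reading, but that reading requires the site to disregard the protocol's own illustration. The narrower meaning of the bracket does not fit its words, which have no limit to elective or non-worsening cases and extend to death.

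The reply is also right to limit the consequences. In-study events are not lost. Section 2.3.4 has the DSMC review all safety and efficacy data, not only SAE listings. Section 7.1 also covers related severe AEs, so it does not rest on SAE status alone. Safety summaries are descriptive under SAP 9, and no efficacy conclusion depends on the SAE count. Death from progression is a remote case: systemic oxalosis is excluded, screening eGFR must be at least 30 mL/min per 1.73 m², and treatment lasts six months.

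What remains unanswered is the 24-hour report, the 30-day window and the accuracy of the serious flag.

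**Conclusion.** The point holds as an inconsistency in an operative safety definition: the examples in 10.3.2 give a classification that the rest of the protocol contradicts. It should be corrected. It does not threaten the primary analysis.

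Three stronger readings are tempting, and the documents do not support them:

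- **That 10.3.2 flatly bars disease-related admissions from being SAEs.** It bars only events that are not AEs, and stone events are AEs.
- **That stone admission is the most likely SAE in this population.** The documents say that patients are predisposed to recurrent stones and give no admission rate.
- **That the SAE table would be distorted by a stated amount.** With the planned 24 and 12 participants, one participant is 1/24 = 4.2 or 1/12 = 8.3 percentage points of an arm. That is true of any event and does not show how many are affected, so no magnitude is claimed.

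The conclusion assumes that some of the approximately 35 sites may act on the example, which cannot be verified from the documents. The documents also do not say how events after Day 180 are collected for participants who enter the extension study, so the 30-day gap may be smaller for them.

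**What to change.** Reconcile 10.3.2 with 10.3.1, 8.1.6.1 and 10.3.3. Remove the bracketed examples from the opening sentence of 10.3.2, and state that stone events, already classed as AEs of special interest, are assessed against the seriousness criteria like any other AE. Tell sites by letter. Before unblinding, query recorded stone events that involved hospitalization for a missing SAE form, and ask sites about stone admissions in the 30 days after the last visit.

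Because related SAEs feed the rule in 7.1, the sponsor should confirm that 7.1 and the reconciled definition agree. No change to that rule is proposed here.

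The cost is one edited passage, a site letter and a limited blinded query. The reported SAE count may rise slightly.

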10.3.3. Definition of Adverse Event of Special Interest

An AESI is a noteworthy event for the particular product or class of products that a Sponsor may wish to monitor carefully ([CIOMS VI, 2005](#)).

Events Meeting the AESI Definition:**Injection site reaction (ISR):**

An ISR is a disorder characterized by an intense adverse reaction (usually immunologic) developing at the site of an injection. Potential ISRs will be graded as follows:

Signs or symptoms at the injection site (e.g., erythema, swelling) with a time to onset of 4 or more hours from the time of study intervention administration will be evaluated according to the Common Terminology Criteria for Adverse Events (CTCAE) v 5.0 criteria for ISR, detailed below. If any of the CTCAE criteria for ISR are met, the event will be recorded as an ISR and graded in accordance with **Table 4**. If the criteria are not met, individual signs or symptoms will be recorded as AEs and graded in accordance with the intensity categories detailed in Section 10.3.4.

Table 4: Grading of Injection Site Reactions, CTCAE v 5.0

Grade 1	Grade 2	Grade 3	Grade 4	Grade 5
Tenderness with or without associated symptoms (e.g., warmth, erythema, itching)	Pain; lipodystrophy; edema; phlebitis	Ulceration or necrosis; severe tissue damage; operative intervention indicated	Life-threatening consequences; urgent intervention indicated	Death

Individual signs or symptoms at the injection site with a time to onset of less than 4 hours from the time of study intervention administration will be recorded as AEs (not as an ISR) and graded in accordance with the intensity categories detailed in Section 10.3.4.

Muscle pain or weakness

Because the nonclinical safety program in mice identified potential off-target effects on skeletal muscle, participants should be monitored for signs and symptoms of muscle weakness or pain, in addition to measurement of plasma CK.

Kidney Stone Events

Patients with PH are predisposed to the development of multiple and recurrent urinary tract and kidney stones. As participants may enter the study with pre-existing stones, stone events (as defined in Section 8.1.6.1), while being considered in the evaluation of efficacy, will be considered AESI.

10.3.4. Recording and Follow-Up of AE and/or SAE**AE and SAE Recording**

- When an AE/SAE occurs, it is the responsibility of the Investigator to review all documentation (e.g., hospital progress notes, laboratory reports, and diagnostics reports) related to the event.
- The Investigator will then record all relevant AE/SAE information in the CRF.
- It is **not** acceptable for the Investigator to send photocopies of the participant's medical records in lieu of completion of the AE/SAE CRF page.
- There may be instances when copies of medical records for certain cases are requested by the Sponsor. In this case, all participant identifiers, with the exception of the participant number, will be redacted on the copies of the medical records before submission.
- The Investigator will attempt to establish a diagnosis of the event based on signs, symptoms, and/or other clinical information. Whenever possible, the diagnosis (not the individual signs/symptoms) will be documented as the AE/SAE.

Assessment of Intensity

The Investigator will make an assessment of intensity for each AE and SAE reported during the study and assign it to one of the following categories:

- Mild: An event that is easily tolerated by the participant, causing minimal discomfort, and not interfering with everyday activities.
- Moderate: An event that causes sufficient discomfort and interferes with normal everyday activities.
- Severe: An event that prevents normal everyday activities. An AE that is assessed as severe should not be confused with a SAE. Severe is a category utilized for rating the intensity of an event, and both AEs and SAEs can be assessed as severe.

An event is defined as 'serious' when it meets at least one of the predefined outcomes as described in the definition of an SAE, NOT when it is rated as severe.

Assessment of Causality

The Investigator is obligated to assess the relationship between study intervention and each occurrence of each AE/SAE.

A "reasonable possibility" of a relationship conveys that there are facts, evidence, and/or arguments to suggest a causal relationship, rather than a relationship cannot be ruled out.

The Investigator will use clinical judgment to determine the relationship.

Alternative causes, such as underlying disease(s), concomitant therapy, and other risk factors, as well as the temporal relationship of the event to study intervention administration will be considered and investigated.

The Investigator will also consult the Investigator's Brochure (IB) and/or Product Information for marketed products in his/her assessment.

For each AE/SAE, the Investigator **must** document in the medical notes that he/she has reviewed the AE/SAE and has provided an assessment of causality.

There may be situations in which an SAE has occurred, and the Investigator has minimal information to include in the initial report. However, **it is very important that the Investigator always make an assessment of causality for every event before the initial transmission of the SAE data to the SAE coordinator.**

The Investigator may change his/her opinion of causality in light of follow-up information and send a SAE follow-up report with the updated causality assessment.

The causality assessment is one of the criteria used when determining regulatory reporting requirements.

The following definitions will be used in assessing causality:

- **Not Related:** Event for which sufficient evidence exists to conclude that the etiology is unrelated to study intervention.
- **Possibly Related:** There is some temporal relationship between the event and the administration of the study intervention, and the event is unlikely to be explained by the participant's medical condition or other therapies.
- **Probably Related:** The temporal relationship between the event and administration of the study intervention is suggestive and the event is unlikely explained by the participant's medical condition or other therapies.
- **Definitely Related:** The event follows reasonable temporal sequence from administration of the study intervention, follows a known or suspected response pattern to the study intervention, is confirmed by improvement upon stopping the study intervention, and reappears upon repeated exposure, if that occurs.

Follow-up of AEs and SAEs

- The Investigator is obligated to perform or arrange for the conduct of supplemental measurements and/or evaluations as medically indicated, or as requested by the Sponsor, to elucidate the nature and/or causality of the AE or SAE as fully as possible. This may include additional laboratory tests or investigations, histopathological examinations, or consultation with other health care professionals.
- If a participant dies during participation in the study or during a recognized follow-up period, the Investigator will provide the Sponsor with a copy of any post-mortem findings, including histopathology.
- New or updated information will be recorded in the originally completed CRF.
- The Investigator will submit any updated SAE data to the Sponsor within 24 hours of receipt of the information.

